**5.2.2. Exclusion Criteria: Part C (Participants with Asthma)**

MEDICAL CONDITIONS	

 
1. Any asthma exacerbation requiring systemic corticosteroids within 8 weeks of screening, or that resulted in overnight hospitalization requiring additional treatment for asthma within 3 months of screening.
 
2. A history of life-threatening asthma, defined as an any asthma episode that required admission to a high-dependency or intensive therapy unit.
 
3. Significant pulmonary diseases, other than asthma, including (but not limited to): pneumonia previously requiring hospital admission, bronchiectasis, pulmonary fibrosis, bronchopulmonary dysplasia, chronic bronchitis, emphysema, chronic obstructive pulmonary disease, or other significant respiratory abnormalities.
 
4. ALT and AST above upper limit of normal (ULN)
 
5. Bilirubin above ULN (isolated bilirubin above x ULN is acceptable if bilirubin is fractionated and direct bilirubin <35%).
 
6. Current or chronic history of liver disease or known hepatic or biliary abnormalities (with the exception of Gilbert's syndrome or asymptomatic gallstones).
 
7. QTcF > 450 msec at screening visit based on the average of triplicate ECGs.
 
8. Signs and symptoms suggestive of COVID-19. 
 
• Note: Assessments will be performed in accordance with local site procedure.
 
 
 
	

 May be repeated once before first dose.

PRIOR/CONCOMITANT THERAPY	

 
9. Past or intended use of over-the-counter or prescription medication, including vitamins, herbal and dietary supplements (including St John's Wort) within 7 days before the first dose of study intervention, unless in the opinion of the Investigator and the GSK Medical Monitor, the medication will not interfere with the study procedures or compromise participant safety. 
 
• Note: Use of SABA, ICS and low dose ICS/LABA and LTRA is permitted for control of Asthma, and use of paracetamol or acetaminophen, at doses <math>\leq</math> 2 g/day and/or simple analgesics is acceptable.
 
 
 
	

PRIOR/CONCOMITANT CLINICAL STUDY EXPERIENCE	

 
10. Participation in this study would result in loss of blood or blood products in excess of 500 mL within 56 days.
 
11. Exposure to more than 4 new chemical entities within 12 months before the first dosing day.
 
12. Current enrolment or past participation in a clinical trial and has received an investigational product within the following time period before the first dosing day in this study: 30 days, 5 half-lives or twice the duration of the biological effect of the investigational product (whichever is longer).
 
	

DIAGNOSTIC ASSESSMENTS	

13. Presence of hepatitis B surface antigen (HBsAg) at screening or within 3 months prior to first dose of study intervention.
 
14. Positive hepatitis C antibody test result at screening or within 3 months prior to first dose of study intervention.
 
 
• Note: Subjects with positive hepatitis C antibody due to prior resolved disease can be enrolled, only if a confirmatory negative hepatitis C RNA test is obtained.
 
 
15. Positive hepatitis C RNA test result at screening or within 3 months prior to first dose of study intervention.
 
 
• Note: Test is optional and subjects with negative hepatitis C antibody test are not required to also undergo hepatitis C RNA testing.
 
 
16. Positive pre-study drug/alcohol screen.
 
17. Positive human immunodeficiency virus (HIV) antibody test.
 
18. Positive test for COVID-19 infection.
 
 
• Note: Testing will be according to site procedures.
 
 
19. Current or history of drug abuse.
	

OTHER EXCLUSIONS	

20. Regular alcohol consumption within 6 months prior to the study defined as:
 
 
• An average weekly intake of > 14 units for males and females.
 
• One unit is equivalent to 8 g of alcohol: a half-pint (~240 mL) of beer, 1 glass (125 mL) of wine or 1 (25 mL) measure of spirits.
 
 
21. Current or previous use of tobacco- or nicotine-containing products (e.g. cigarettes, nicotine patches or electronic devices) within 6 months before screening and/or have a smoking pack history of > 5 pack years.
 
 
• Note: 1 pack year = 20 cigarettes per day for 1 year or 5 cigarettes per day for 4 years.
 
 
22. Positive breath carbon monoxide test indicative of recent smoking at screening or each in-house admission to the clinical research unit.
 
23. Sensitivity to any of the study interventions, or components thereof (including lactose and magnesium stearate (MgSt)), or drug or other allergy that, in the opinion of the investigator or medical monitor, contraindicates participation in the study.
 
24. Participants with known COVID-19 positive contacts in the past 14 days.
	

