##### TYPE OF PARTICIPANT

2. Participants who are otherwise healthy (other than the acceptable condition of asthma and other mild atopic diseases, including allergic rhinitis and atopic dermatitis) as determined by medical evaluation based on screening medical history, physical examination, vital signs, ECG assessment, pulmonary function testing, laboratory tests and cardiac monitoring.
  - **Note:** A participant with a clinical abnormality or laboratory parameter(s) not specifically listed in the exclusion or exclusion criteria that is outside the reference range for the population being studied may be included only if the investigator, in consultation with the Medical Monitor (if required), agree and document that the finding is unlikely to introduce additional risk factors and will not interfere with the study procedures.
3. A current confirmed physician diagnosis of asthma (as defined by the British Thoracic Society/ Scottish Intercollegiate Guidelines Network ([BTS/SIGN](#), 2019), or the Global Initiative for Asthma ([GINA](#), 2020 guidelines)) at least 6 months before screening. The reason for diagnosis of asthma should be documented in the participant's source data, including relevant history.

4. A screening pre-bronchodilator FEV1  $\geq$  65% predicted normal value.  
**Note:** Predicted values based on European Respiratory Society (ERS) guidelines [Quanjer, 2012].

5. Participants with maintained control of their asthma using the permitted medications listed below, will be recruited as follows:

Permitted Medication Use	Number of Participants
SABA use and/or intermittent ICS/LABA use.	n=8
Regular treatment with ICS or ICS/LABA (including use of Leukotriene Receptor Agonist (LTRA))	n=8

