## MEDICAL CONDITIONS

1. History or presence of cardiovascular, respiratory, hepatic, renal, gastrointestinal, endocrine, hematological, or neurological disorders capable of significantly altering the absorption, metabolism, or elimination of drugs; constituting a risk when taking the study intervention or interfering with the interpretation of data.
2. Alanine transaminase (ALT) and Aspartate Aminotransferase (AST) above upper limit of normal (ULN).
3. Total Bilirubin above ULN (isolated bilirubin above ULN is acceptable if total bilirubin is fractionated and direct bilirubin <35%).
4. Current or chronic history of liver disease or known hepatic or biliary abnormalities (with the exception of Gilbert's syndrome or asymptomatic gallstones).
5. QTcF > 450 msec at screening visit based on the average of triplicate ECGs.
6. Screening ECG measurements meets the following criteria for exclusion:

Parameter	Males	Females
Heart Rate	< 45 or > 100 bpm	< 50 or > 100 bpm
PR Interval	< 120 or > 220 msec	
QRS duration	< 70 or > 120 msec	
QTcF	> 450 msec	

- **Note:** A heart rate from 100 to 110 bpm can be rechecked by ECG or vital signs within 30 minutes to verify eligibility.
- 7. Medical history of cardiac arrhythmias or cardiac disease or a family or personal history of long QT syndrome.
- 8. Evidence of previous myocardial infarction (does not include ST segment changes associated with re-polarization).
- 9. Signs and symptoms suggestive of COVID-19.
  - **Note:** Assessments will be performed in accordance with local site procedure.

 May be repeated once before first dose.

PRIOR/CONCOMITANT THERAPY

10. Past or intended use of over-the-counter or prescription medication, including vitamins, herbal and dietary supplements (including St John's Wort) within 7 days before the first dose of study intervention, unless in the opinion of the Investigator and the GSK Medical Monitor, the medication will not interfere with the study procedures or compromise participant safety.
 

• Note: Use of paracetamol or acetaminophen, at doses <math>\leq 2</math> g/day and/or use of simple analgesics is acceptable.

PRIOR/CONCOMITANT CLINICAL STUDY EXPERIENCE

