
11. Participation in this study would result in loss of blood or blood products in excess of 500 mL within 56 days.
 
12. Exposure to more than 4 new chemical entities within 12 months before the first dosing day.
 
13. Current enrolment or past participation in a clinical trial and has received an investigational product within the following time period before the first dosing day in this study: 30 days, 5 half-lives or twice the duration of the biological effect of the investigational product (whichever is longer).

DIAGNOSTIC ASSESSMENTS	
14.	FEV1 and FVC < 80% predicted normal value. 

• Note: Predicted values based on European Respiratory Society (ERS) guidelines [Quanjer, 2012].

15.	Presence of hepatitis B surface antigen (HBsAg) at screening or within 3 months prior to first dose of study intervention.
16.	Positive hepatitis C antibody test result at screening or within 3 months prior to first dose of study intervention. 

• Note: Subjects with positive hepatitis C antibody due to prior resolved disease can be enrolled, only if a confirmatory negative hepatitis C RNA test is obtained

17.	Positive hepatitis C RNA test result at screening or within 3 months prior to first dose of study intervention. 

• Note: Test is optional and subjects with negative hepatitis C antibody test are not required to also undergo hepatitis C RNA testing

18.	Positive pre-study drug/alcohol screen.
19.	Positive human immunodeficiency virus (HIV) antibody test.
20.	Positive test for COVID-19 infection. 

• Note: Testing will be according to site procedures.

21.	Current or history of drug abuse.
22.	Any conduction abnormality (including but not specific to left or right complete bundle branch block, AV block [2nd degree or higher], Wolff-Parkinson-White (WPW) syndrome).
23.	Sinus Pauses > 3 seconds.
24.	Any significant arrhythmia which, in the opinion of the Investigator or GSK Medical monitor, will interfere with the safety for the individual participant.
25.	Non-sustained or sustained ventricular tachycardia (with more than 3 consecutive ventricular ectopic beats).

OTHER EXCLUSIONS

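### Part C has no PR, QRS or conduction exclusion, so findings that bar entry to Parts A and B are left to investigator judgement

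*Protocol*

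**What the plan says.** Protocol 5.2.1, which is headed for Parts A and B only, deals with the ECG in several places. Criterion 5 excludes on QTcF. Criterion 6 opens "Screening ECG measurements meets the following criteria for exclusion" and gives limits for four parameters: heart rate, PR ("< 120 or > 220 msec"), QRS (below 70 or above 120 msec) and QTcF. Criterion 22 excludes "Any conduction abnormality (including but not specific to left or right complete bundle branch block" and goes on to name second-degree or higher AV block and Wolff-Parkinson-White syndrome. Cardiac history is covered by criterion 7 ("Medical history of cardiac arrhythmias or cardiac disease or a family or personal history of long QT syndrome") and criterion 8 ("Evidence of previous myocardial infarction").

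Protocol 5.2.2, for Part C, runs from 1 to 24 with no gap in numbering and no redaction mark. Its one cardiac item is criterion 7, QTcF above "450 msec at screening visit based on the average of triplicate ECGs".

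Beyond that, Part C relies on inclusion criterion 2 in 5.1.2. It calls for "Participants who are otherwise healthy (other than the acceptable condition of asthma and other mild atopic diseases", judged on history, examination, vital signs, ECG and cardiac monitoring among other assessments. Its note covers abnormalities that the criteria do not name. A participant with one "may be included only if the investigator, in consultation with the Medical Monitor (if required), agree and document that the finding is unlikely" to add risk and will not interfere with study procedures.

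**The concern.** The note to inclusion 2 operates only on findings that the criteria do not name, so leaving a finding off the 5.2.2 list is what opens the discretionary route. Complete bundle branch block, a PR interval of 230 msec or a QRS duration of 130 msec ends eligibility in Parts A and B. In Part C each is a judgement call.

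The lighter list applies to the older population: the age cap is 65 rather than 50. The Part B safety data reviewed before Part C starts come from people who had to pass the PR, QRS and conduction criteria, so those data say nothing direct about people who would fail them. At stake is who may be dosed at the planned 3000 mcg daily, and whether that decision is made the same way for each participant. This is a safety-entry point, and the analysis is not affected in any way the documents allow one to demonstrate.

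**Working it through.** No plan figure needs reproducing. The check is a comparison of criteria.

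**Step 1. Does 5.2.1 also apply to Part C?** No. Its heading limits it to Parts A and B, and 5.2.2 repeats the shared items (liver tests, hepatitis, HIV, alcohol, smoking, COVID-19). A list that repeats shared items is meant to stand alone.

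**Step 2. Match the ECG and cardiac criteria.**

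| Item | Parts A/B (5.2.1) | Part C (5.2.2) |
|---|---|---|
| QTcF > 450 msec | criteria 5 and 6 | criterion 7 |
| PR < 120 or > 220 msec | criterion 6 | none |
| QRS < 70 or > 120 msec | criterion 6 | none |
| Heart rate < 45 (men), < 50 (women) or > 100 bpm | criterion 6 | none |
| Conduction abnormality | criterion 22 | none |
| Arrhythmia, cardiac disease, long QT history | criterion 7 | none listed |
| Previous myocardial infarction | criterion 8 | none listed |

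Of the 4 parameters in criterion 6, Part C keeps 1, so 4 - 1 = 3 are absent.

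**Step 3. Which absences matter?**
- Criteria 7 and 8 concern known disease. A person with cardiac disease or a past infarction would hardly pass as otherwise healthy when only asthma and mild atopic disease are excepted. Inclusion 2 largely covers these.
- Heart rate is a clinical trade-off in people using beta-agonists. A healthy-volunteer cut-off may not suit them.
- PR, QRS and conduction findings can be isolated ECG results in someone who is otherwise well. That is the kind of finding the note allows in.

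This leaves 2 limits (PR, QRS) and 1 criterion (22).

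**Step 4. Is the general health wording enough for those three?** Parts A and B have an equivalent inclusion 2 with the same note (5.1.1), and the sponsor still added explicit limits there. The general wording was not treated as sufficient in the younger group. The difference in age cap is 65 - 50 = 15 years.

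**Step 5. Could Part C apply the limits with the data it collects?** Yes. The screening schedule is common to Parts A, B and C and includes a triplicate 12-lead ECG. Section 8.1.3.2 requires machines that report PR and QRS. The Part C schedule also has an eligibility review on Day -1, alongside a further 12-lead ECG.

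**The case against.** The strongest reply is that Part C entry is already controlled. Inclusion 2 is mandatory, an unlisted abnormality enters only on a documented judgement that added risk is unlikely, and eligibility is reviewed again on Day -1 with a fresh ECG, a row that the Part A and B treatment schedules do not show. This stands in part: it narrows the gap and lowers the priority. It does not close it, because both steps apply judgement where Parts A and B apply a fixed rule.

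A second reply is that the fuller list in Parts A and B may serve ECG work that is redacted; parts of section 8.1.3 are blacked out. This is possible, so the lack of a stated reason is not held against the plan. Whatever the reason for setting them, the PR and QRS limits and criterion 22 can be applied to the ordinary screening ECG.

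A third is that the visible drug risks in section 2.3.1 are bronchospasm and airway irritancy, with no cardiac hazard. That stands.

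Some stronger readings might be inferred, and the documents do not support them:
- *Part C monitoring is too thin to catch an admitted abnormality.* On the schedules as extracted, Part C has ECGs on 5 of 7 dosing days (71%) and Part B on 8 of 14 (57%), both pre-dose and at 6 hours, with telemetry for the first dose only in each. Monitoring does not single out Part C.
- *Part C lacks a needed sentinel step.* Section 4.2 reserves sentinels for dose levels new to humans, and the Part C dose may not exceed the Part B dose.
- *A given share of the 16 participants will carry such a finding.* That needs a prevalence, and none is given.
- *The clinically significant ECG table will be distorted.* That depends on ranges held in a separate programming specification that was not supplied.

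**Conclusion.** The point holds as a cheap improvement of low priority. Two numeric ECG limits and one conduction criterion that exclude outright in Parts A and B have no counterpart in Part C, where the age cap is 15 years higher and the same findings can be admitted on documented investigator judgement. The conclusion rests on reading 5.2.2 as self-contained and on the note to inclusion 2 applying to any finding the criteria do not name; the text supports both.

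A reader might take this to mean that Part C has no cardiac screening beyond QTcF. It does have it, through inclusion 2 and the Day -1 review; what is missing is explicit limits. Nor do the documents show that anyone would be harmed, or how many would be affected.

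**What to change.** Add to 5.2.2 the PR and QRS limits of 5.2.1 criterion 6 and the conduction exclusion of criterion 22. Apply them to the triplicate 12-lead ECG taken at screening and recheck them at the existing Day -1 eligibility review. Leave the heart rate limit to the sponsor's clinicians because of beta-agonist use. Criteria 7 and 8 need not be added.

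The change is to wording only, with no new test, visit or equipment. The cost is preparing the amendment and obtaining its approval, and possibly a few more screen failures, a number the documents do not allow one to estimate.

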### 5.3. Lifestyle Considerations

#### 5.3.1. Meals and Dietary Restrictions

- Refrain from consumption of Seville oranges, grapefruit or grapefruit juice, pomelos, exotic citrus fruits, grapefruit hybrids from 7 days before the start of study intervention until discharge from the unit.

- No water is allowed until 2 hours after dosing, water is allowed ad libitum at all other times.
- Participants must fast overnight until 2 hours after each dose.

### **5.3.2. Caffeine, Alcohol, and Tobacco**

- During each dosing session, participants will abstain from ingesting caffeine- or xanthine-containing products (e.g., coffee, cola drinks, and chocolate) for 12 hours before the start of dosing until after collection of the final pharmacokinetic (PK) sample.
- During each dosing session, participants will abstain from alcohol for 24 hours before the start of dosing until after collection of the final PK sample.
- Participants who use tobacco or nicotine-containing products are not eligible for this study, See Section [5.2](#).

### **5.3.3. Activity**

- Participants will abstain from strenuous exercise for 72 hours before each blood collection for clinical laboratory tests. Participants may participate in light recreational activities during the study.

## **5.4. Screen Failures**

Screen failures are defined as participants who consent to participate in the clinical study but are not subsequently randomised. A minimal set of screen failure information is required to ensure transparent reporting of screen failure participants to meet the Consolidated Standards of Reporting Trials (CONSORT) publishing requirements and to respond to queries from regulatory authorities. Minimal information includes demography, screen failure details, eligibility criteria, any protocol deviations and any SAEs.

Individuals who do not meet the criteria for participation in this study (screen failure) may be rescreened once. Rescreened participants should be assigned a new participant number for every screening/rescreening event. Unused reserve participants that meet eligibility criteria are not considered screen failures.

## **6. STUDY INTERVENTION(S) AND CONCOMITANT THERAPY**

Study intervention is defined as any investigational intervention(s), marketed product(s), placebo, or medical device(s) intended to be administered to a study participant according to the study protocol.

## 6.1. Study Intervention(s) Administered

ARM Name	Cohort 1	Cohort 2	Cohort 3,4	Cohort 5	Cohorts 1-5
Intervention Name	GSK3923868 Capsules for Inhalation	GSK3923868 Capsules for Inhalation	GSK3923868 Capsules for Inhalation	GSK3923868 Capsules for Inhalation	Placebo to match GSK3923868 Capsules for Inhalation
Type	Drug	Drug	Drug	Drug	Placebo
Dose Formulation	Capsule containing Inhalation powder blend Delivered via Monodose RS01 device	Capsule containing Inhalation powder blend Delivered via Monodose RS01 device	Capsule containing Inhalation powder blend Delivered via Monodose RS01 device	Capsule containing Inhalation powder blend Delivered via Monodose RS01 device	Capsule containing Inhalation powder blend Delivered via Monodose RS01 device
Unit Dose Strength(s)	50 mcg	500 mcg	500 mcg	500 mcg	N/A
Dosage Level(s)	50 mcg: one capsule, single dose 100 mcg: two capsules, single dose 250 mcg: five capsules, single dose	500 mcg: one capsule, single dose 1000 mcg: two capsules, single dose 3000 mcg: six capsules, single dose	Planned dose: 3000 mcg: six capsules, daily for 14 days	Planned dose: 3000 mcg: six capsules, daily for 7 days	Number of capsules to match active treatment
Route of Administration	Inhalation	Inhalation	Inhalation	Inhalation	Inhalation
Use	Experimental	Experimental	Experimental	Experimental	Placebo
IMP and NIMP	IMP	IMP	IMP	IMP	IMP
Sourcing	Provided centrally by the Sponsor	Provided centrally by the Sponsor	Provided centrally by the Sponsor	Provided centrally by the Sponsor	Provided centrally by the Sponsor

ARM Name	Cohort 1	Cohort 2	Cohort 3,4	Cohort 5	Cohorts 1-5
Packaging and Labelling	Study Intervention will be provided in a HDPE (high density polyethylene) bottles.  Each bottle contains 21 capsules and one 8 g 20%RH maintaining desiccant sachet.  Each bottle will be labelled as required per country requirement.	Study Intervention will be provided in HDPE bottles.  Each bottle contains 32 capsules and one 8 g 20%RH maintaining desiccant sachet.  Each bottle will be labelled as required per country requirement.	Study Intervention will be provided in HDPE bottles.  Each bottle contains 32 capsules and one 8 g 20%RH maintaining desiccant sachet.  Each bottle will be labelled as required per country requirement.	Study Intervention will be provided in HDPE bottles.  Each bottle contains 32 capsules and one 8 g 20%RH maintaining desiccant sachet.  Each bottle will be labelled as required per country requirement.	Study Placebo will be provided in HDPE bottles.  Each bottle contains 32 capsules and one 8 g 20%RH maintaining desiccant sachet.  Each bottle will be labelled as required per country requirement.
Current Name	N/A	N/A	N/A	N/A	N/A

 Any unplanned doses of GSK3923868 will be administered using combinations of 50 and 500 mcg capsules as necessary.

### 6.1.1. Medical Devices

- The GSK manufactured medical devices (or devices manufactured for GSK by a third party) provided for use in this study are the Monodose RS01 (manufacturer Plastiape S.p.A)
- Instructions for medical device use are provided in the Study Reference Manual (SRM).
- All device deficiencies, (including malfunction, use error and inadequate labelling) shall be documented, and reported by the Investigator throughout the clinical investigation (see Section 8.2.7) and appropriately managed by the Sponsor.

